3.3.14 Quantitative Collection and Analysis

The following questionnaires will be completed at three times; before, six weeks into the trial and six months after the trial. Teachers, parents and children will complete the Strengths and Difficulties Questionnaires, Developmental Behaviour Checklist, and the generalisability questionnaire about the children. Parents will complete the General Health Questionnaire about themselves. The target behaviour will be agreed at the beginning of treatment and the outcome questionnaire completed at 6 weeks and six months into the trial.

This will enable us to examine the change in behaviour scores over the course of the intervention and monitor whether the skills learnt are maintained over a longer period.

Change in parental stress will be measured using the General Health Questionnaire at the beginning, midpoint and end of the trial. We will also assess acceptability to parents and teachers using a 12 item Intervention Rating Profile at the end of the study. We will examine the effects of diagnosis and age of the participants when carrying out the analysis. Qualitative interviewing will take place to obtain feedback about acceptability and utility to parents and carers.

We are carrying out a feasibility study to assess parameters such as:

- willingness of children and young people and their parents to participate
- issues around consent and assent in children and young people with ASD
- acceptability of the intervention with children, young people and families
- acceptability of not receiving the intervention
- qualitative aspects around the process of delivery of the intervention including who delivers it and how it is formulated, when and how it is delivered and for how long
- acceptability of training for teachers and other staff, and the feasibility of arranging an delivering training in a busy school environment (e.g. release for training)
- follow up and response rates
- attrition and non compliance rates
- characteristics and utility of the outcome measures

At this point we have not chosen a main outcome measure as it is one of the purposes of the feasibility study to explore which outcome measures are most likely to be useful, which may include:

- 1. Developmental Behaviour Checklist (DBC; (49)), which includes ASD subscales and a disruptive subscale (parent and teacher)
- 2. Strengths and Difficulties Questionnaire (SDQ; (50)), which includes conduct, hyperactivity and prosocial subscales (parent, child, teacher)
- 3. Likert Scales for target behaviours designed and agreed by the focus groups/ expert panel (parent, child, teacher, and clinician). In this way we will develop a goal based outcomes scale and test its usefulness against the other instruments as part of our feasibility study.
- 4. Generalisability will be assessed using questionnaires designed for each individual child that ask about the frequency of challenging behaviours for both the Social Story target behaviour and for other associated or related behaviours (e.g. if more positive behaviours in the class result in reduced destruction in the class are there also reductions seen in other settings, such as the dining hall, home etc). These will be parent and teacher based questionnaires used before and after the intervention.

- 5. General Health Questionnaire (parents)
- 6. Intervention Rating Profile (51), which has been widely used to assess parents views of interventions used with their children. A separate questionnaire will be developed to be administered by parents to their child to assess the views and experiences of the child of using Social Stories.

Descriptive statistics will be calculated for recruitment rates, follow-up rates and attrition. Descriptive statistics and 95% confidence intervals will be calculated for the outcome measures. We will use the data to develop estimates for a fully powered RCT that will include estimates of change in outcome measures over time taking into account attrition and follow up rates.

Although the feasibility study is not powered to detect differences in outcome measures we will undertake inferential statistics (Chi-squared tests for categorical data, t- tests for continuous data, and Mann-Whitney tests for ordinal data). All analyses will be undertaken on SPSS version 17.

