Target Population: Children (aged 4-15) in mainstream school settings with a diagnosis of ASD according to ICD-10 research diagnostic criteria (WHO, 1993), ADI-R (Lord et al, 1994) and ADOS (Lord et al, 2000), who exhibit challenging behaviour in the school setting. This will be assessed using instruments informed by the systematic review (examples include the Strengths and Difficulties Questionnaire (SDQ) and the Developmental Behaviour Checklist (DBC)). We will also set a clear goal with the child, family and teacher and rate it using Likert scales before and after the study. Schools will be approached through an existing network of clinical and educational practitioners and researchers led by co applicant [name].

Intervention: A manualised toolkit of appropriate Social Stories for use with school aged children exhibiting challenging behaviour within the mainstream school setting. The toolkit and exact methodology of the feasibility study will be determined in earlier phases of the study. The comparator treatment will be an attention control.

Both arms will receive treatment as usual, for example, behavioural approaches, parenting support, systemic approaches and social skills training.

Outcomes: Primary Outcomes: utility and acceptability to parents/teachers/children of using the manualised Social Stories intervention in a mainstream school setting, as assessed by qualitative interviews and questionnaires. Secondary Outcomes: Acceptability of the research methods (e.g. randomisation procedure) to parents /carers /teachers/ children. Standard deviations of the measures used (e.g. SDQ, DBC, Likert Scales) in the two groups (Social Stories and attention control) to inform power calculation.

Economic Evaluation: The economic evaluation will take the form of within-trial costeffectiveness analysis that will determine the incremental cost per unit of effectiveness measure for Social Stories compared with an attention control in children with autism.

Sample Size: 10 parents, 5 children/young people, 5 teachers and 5 non research clinicians will be involved in the qualitative interview phase. The manualised intervention will be delivered to 25 children (and 25 children in the control group) in our feasibility study, where we will demonstrate recruitment, attrition and follow up rates, with preliminary estimates of effect size to inform sample size calculations for a full trial.

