3.3.4 Randomization

We will adopt a cluster randomization approach. This is to minimize the likelihood of participants in the different intervention groups being affected by changes in teacher or school behaviour. It also recognizes that social story expertise within a school is likely to be enhanced by sharing of skills and networking of ideas, and this design therefore more accurately reflects what would happen if social stories were used within a school in practice. We will use the qualitative interviewing within the feasibility design to explore this further, as described below.

To reduce detection bias we will first recruit the mainstream schools to be involved in the study. Then subsequently we will consent children and their families within these selected schools for involvement in the study. Only then will we randomize the schools into schools where the intervention takes place and those where it does not but where we are monitoring outcomes in the same way as in the intervention school. Participants will be randomised at whole school level, thus all children with ASD within any given school will be randomised to the same arm of the trial. This will minimize contamination as the likelihood of participants in the different intervention groups being affected by changes in teacher or school behaviour will be reduced. In order to limit detection bias, participants will be receive the Social Story intervention. The control school children will receive an equivalent amount of time reading a story of similar length and linguistic complexity a range of which will be chosen by the expert panel as an attention control. In both schools children will receive all other treatment or support as usual and we will monitor carefully what this is.

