3.3.5 Trial Intervention

Schools will be randomised to one of two arms; the intervention group and the control group. Prior to the intervention teachers and parents of children in the intervention group will undertake training on Social Stories. We will run Social Stories training workshops informed by the earlier parts of the study. The Social Stories will be delivered in a way that is informed by the pre clinical theory and phase 1 of this study using the most promising mode of delivery. This will include who designs the Social Story with parent and child, how this is achieved, and how and when the Social Story is delivered with the child. For example this could include a teacher, support assistant, special educational needs coordinator and /or a parent and they will receive support as part of the study from the clinical researchers. The precise from of this support will be designed using findings from the pre clinical theory and phase 1 of this study.

We will check the construction of the Social Stories paying particular attention to construction guidelines as laid down by the original Social Stories model. We will also explore any other parameters, including construction, content and delivery that have been found to be related to outcome as part of the systematic review and user and expert panels. As part of this, for example, we will measure goals of the intervention, intervention agents, intervention setting, timings of the intervention, length of the intervention and number of stories per child. We will also assess characteristics such as the number and distribution of pictures and photographs, and the length and complexity of sentences, types of behaviours described and any allied interventions or support.

Whatever the precise methodology we will keep a record of all the design interactions and precise number, timings and locations of delivery. We will also record attrition, non

compliance and any distress. We will have a clear methodology of how to deal with any difficulties including child distress.

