3.3.11 Blinding

Blinding of the participants will not be feasible, nor is blinding of all members of the study team who are actively involved in the administration of the study. However, members of the study team responsible for the statistical analysis will be kept blind to group allocation.

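### The individual target behaviour is fixed when treatment starts, which falls after school randomisation, and its baseline rating is not scheduled consistently

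*Protocol*

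**What the plan says.** Four parts of the protocol bear on this.

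- **Setting and rating the goal.** Section 3.3.14 states: "The target behaviour will be agreed at the beginning of treatment". It has "the outcome questionnaire completed at 6 weeks and six months into the trial". The Summary (Target Population) says that the child, family and teacher will set a goal and "rate it using Likert scales before and after the study".
- **Other instruments.** For the SDQ, the DBC, the generalisability questionnaire and the parents' GHQ, section 3.3.14 says: "The following questionnaires will be completed at three times; before, six weeks into the trial and six months after the trial". Item 4 of its list has the generalisability form designed for each child, asking about "the frequency of challenging behaviours for both the Social Story target behaviour and for other associated or related behaviours", and used both before and after the intervention.
- **Order of steps.** Section 3.3.4 recruits schools, then consents families, and continues: "Only then will we randomize the schools into schools where the intervention takes place and those where it does not". Section 3.3.5 adds: "Prior to the intervention teachers and parents of children in the intervention group will undertake training on Social Stories".
- **Blinding.** Section 3.3.11 states: "Blinding of the participants will not be feasible". Only those doing the statistical analysis are kept blind.

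Item 3 of the list in section 3.3.14 makes the Likert rating of target behaviours (by parent, child, teacher and clinician) a goal-based outcome scale, whose usefulness is to be tested against the other instruments.

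**The concern.** A goal-based outcome compares arms fairly only if the goals were chosen without knowledge of the arm. If they are chosen afterwards, the two arms may be rating different kinds of behaviour: more tractable ones, or ones better suited to a story, in one arm than in the other. A difference could then appear with no treatment effect, and the goal scale could look more responsive than the SDQ or DBC for the wrong reason.

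This matters even though the study is only a feasibility trial. One of its stated purposes is to find out which outcome measure to use. The Summary takes the standard deviations in the two groups forward to a power calculation, and section 3.3.10 takes preliminary effect sizes forward to the full trial's sample size. Section 3.3.14 also plans between-arm tests. A measurement artefact here would carry over into the design of the full trial.

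The baseline schedule is a second, separate matter. Change on the goal scale needs a rating before treatment, and the section that sets the schedule does not give one for that questionnaire.

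**Working it through.** The protocol gives no figure on this point, so the check is one of sequence.

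**Step 1: order of events.**

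| Order | Event | Source |
|---|---|---|
| 1 | Schools recruited | 3.3.4 |
| 2 | Families consented; children screened against the behaviour cut-offs | 3.3.4, 3.3.9, 4.3 |
| 3 | Schools randomised | 3.3.4 |
| 4 | Intervention-arm teachers and parents trained | 3.3.5 |
| 5 | Treatment begins; target behaviour agreed | 3.3.14 |
| 6 | Target-behaviour outcome questionnaire at 6 weeks and six months | 3.3.14 |

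Treatment cannot begin before step 3, so a target agreed when treatment begins is agreed after allocation. By then the intervention-arm teachers and parents have been trained, so they know their arm. No section places goal-setting at step 2. That allocation is known when the goal is set is an inference from sections 3.3.4, 3.3.5 and 3.3.11; section 3.3.14 does not say so.

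**Step 2: is there a baseline rating?**

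| Source | Timing of the rating |
|---|---|
| Summary | Goal rated before and after the study |
| 3.3.14, target-behaviour outcome questionnaire | 6 weeks and six months only |
| 3.3.14, generalisability form (three-time schedule and item 4) | Includes a time point before |

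The first two rows conflict. The third conflicts with the timing of the goal: a form written for one child and built around that child's target cannot be completed before the target is known. Section 3.3.14 does not name the instrument behind the target-behaviour outcome questionnaire; I take it to be the Likert scale of item 3.

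**Step 3: what is affected.** The timing of the choice touches two of the six listed measures: the goal-based Likert scale (four rater versions) and the generalisability form. The missing baseline time point touches only the target-behaviour outcome questionnaire, because the generalisability form has one.

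**Step 4: illustration of consequence, on assumed shifts.** Assume 25 children per arm (from the Summary), no clustering, no true effect, and a between-arm shift of b standard deviations caused only by the choice of goal. The chance that a two-sided 5% test is significant is

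Φ(b/√(2/25) − 1.96) + Φ(−b/√(2/25) − 1.96), with √(2/25) = 0.283.

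- b = 0.2: Φ(−1.25) + Φ(−2.67) = about 11%
- b = 0.3: Φ(−0.90) + Φ(−3.02) = about 19%
- b = 0.5: Φ(−0.19) + Φ(−3.73) = about 42%

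Without any shift it would be 5%. The values of b are assumptions, and nothing in the protocol supports one over another.

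**The case against.** The strongest reply is that the start of treatment is loose wording for the baseline assessment. Section 3.3.14 is not careful with such terms: it gives the GHQ a time point before the trial and, a little later, one at its beginning. The Summary describes goal-setting next to the screening instruments, and the generalisability form could not be completed beforehand unless the target were already set. This is a fair reading and lowers the certainty. It does not settle the matter, because neither the Summary nor section 3.3.14 says that baseline precedes randomisation, and the literal text points the other way. The content of the timeline in Appendix Three is not visible, so it cannot be checked.

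Three stronger readings are tempting, and the protocol does not support them.

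- **Change on the goal cannot be computed.** A reader of section 3.3.14 alone might infer this. But the Summary plans a Likert rating before the study, and item 4 plans a pre-intervention form that covers the target.
- **Trained raters will pick story-friendly goals.** The protocol does not say this. Sections 3.2.3 and 5.0 describe guidance that starts once a challenging behaviour has been identified, and section 3.3.9 requires such behaviour before randomisation. The same sections add that the story's focus may differ from the behaviour itself, so training could influence the choice. Its influence is possible, not shown.
- **Control children have no target.** The wording of item 4 suggests it, but goal-setting in the Summary is not limited to one arm, and section 3.3.4 says that outcomes are monitored alike in both sets of schools.

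It is also true that no main outcome has been chosen, that the study is not powered for outcome differences, and that unblinded rating would remain after any change to goal-setting. These points limit the severity. They do not remove the reason to fix a step that no later analysis can repair.

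**Conclusion.** The point holds in a limited form. On the protocol's own order of steps, the target behaviour is agreed after school randomisation and after intervention-arm training, by people who are not blinded. The choice of goal may therefore differ by arm and could bias a candidate main outcome. Separately, the Summary and section 3.3.14 do not agree on when the goal is first rated; a baseline rating is planned but not consistently scheduled.

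The conclusion rests on reading the start of treatment literally, and on the absence of any statement that puts goal-setting before randomisation. The size of any bias cannot be estimated from the protocol; the 11% to 42% above shows only what assumed shifts of 0.2 to 0.5 SD would do. The change is worth making because it is cheap and protects figures that feed the full trial. It is not evidence that the feasibility results will be biased.

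**What to change.** Amend section 3.3.14 as follows.

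1. Agree and rate the target behaviour, and the related behaviours for the generalisability form, at a baseline visit after consent and before the school is randomised, by the same procedure in both arms.
2. Rate the same behaviours unchanged at each follow-up.
3. Reconcile the Summary, the schedule in section 3.3.14 and its item 4, so that the target-behaviour questionnaire has an explicit baseline time point.
4. Replace the term for the target in item 4 with one that fits both arms.
5. If the story's focus later differs from the pre-set goal, record this and keep the pre-randomisation goal as the outcome.

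Adding a baseline rating without moving the choice of goal would not be enough, because the goal could still depend on the arm.

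The cost is modest. Families are already met for consent and children already screened before randomisation (sections 3.3.4, 3.3.9 and 4.3), so an existing step moves earlier. The real downside is that the trial may rate a goal that the story does not directly address, which sections 3.2.3 and 5.0 suggest can happen; recording the divergence shows how often it does. Knowledge of the arm when ratings are made is not cured by this change and should be stated as a limitation.

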3.3.7 Withdrawal

Withdrawal can occur at any point during the study at the request of the participant. If a participant indicates they wish to withdraw from the study, withdrawal will be clarified as to whether the withdrawal is from the intervention, from follow-up or all aspects of the study. Where withdrawal is only from the intervention then follow-up data will continue to be collected. Data will be retained for all participants up to the date of withdrawal, unless they specifically request for their details to be removed.

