3.3.13 Qualitative Study

There has been little previous qualitative work exploring issues of effectiveness and acceptability of Social Stories amongst this population. An in depth appreciation of these issues will be essential for any future implementation of the manualised intervention if it proves to be clinically and cost effective. This process evaluation we will examine using semi-structured interviews, which behaviours are most problematic to children, their families and teaching staff, expectations of the technique and which of the treatment outcomes are of greatest importance to children, their families and teachers. In addition, data will be collected on the pilot trial process itself. We will ask questions relating to the acceptability of the treatment, the randomisation procedure and the methods of data collection. We will also explore qualitatively the experiences of the teachers in the context of the cluster randomisation design. We will be particularly interested in comparing those schools where several children have used the intervention compared to schools where smaller numbers of children are involved. We are interested in the systemic and individual effects. All interviews will be conducted using a topic guide to ensure consistency across participants, however, the format will be flexible in order to allow participants to generate naturalistic data on what they constitute as important and/or successful in terms of treatment outcomes.

It is anticipated a sample of 15 children and an associated family member (10 from the intervention arm and 5 from the usual care arm) would provide sufficient data to answer these questions. Trial participants will be purposively sampled on characteristics such as age, gender, extent of behavioural problems. All participants would be interviewed after the writing of the Social Story face-to-face at a location convenient for the participants with the family members; this would enhance rapport and facilitate data collection.

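### Acceptability, a primary outcome, is rated once at the end of the study, so those who leave follow-up give no rating and the result risks being too favourable

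*Protocol*

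**What the plan says.** The Summary of the protocol gives the primary outcome as "utility and acceptability to parents/teachers/children of using the manualised Social Stories intervention in a mainstream school setting, as assessed by qualitative interviews and questionnaires".

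- **Rating scale for adults.** Section 3.3.14: "We will also assess acceptability to parents and teachers using a 12 item Intervention Rating Profile at the end of the study". No other occasion is given.
- **Child's form.** Section 3.3.14, item 6: "A separate questionnaire will be developed to be administered by parents to their child to assess the views and experiences of the child". No time point is stated.
- **Training.** Section 3.3.5: "Prior to the intervention teachers and parents of children in the intervention group will undertake training on Social Stories". The same section names a parent among those who might deliver the story, and section 3.3.13 plans interviews with five parents or carers who deliver it.
- **Interviews.** Section 3.3.13 plans interviews with 15 children, each with a family member: 10 from the intervention arm and 5 from the control arm. On content: "We will ask questions relating to the acceptability of the treatment, the randomisation procedure and the methods of data collection". On timing: "All participants would be interviewed after the writing of the Social Story face-to-face". On selection: "Trial participants will be purposively sampled on characteristics such as age, gender, extent of behavioural problems". Five professionals and the five delivering parents or carers are also asked why, in their view, any participant discontinued.
- **Withdrawal.** Section 3.3.7: "withdrawal will be clarified as to whether the withdrawal is from the intervention, from follow-up or all aspects of the study". Follow-up continues for those who stop only the intervention. Under section 3.3.12, data from a participant lost to follow-up are used up to the point of loss, and attempts are made to contact that participant.

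**The concern.** People who find an intervention unacceptable are plausibly more likely than others to leave. A scale given once, after an intervention lasting 4-6 months (section 3.3.8), cannot record the view of someone who has left follow-up by then. The section 3.3.12 rule of using data up to the point of loss does not help, because an end-only instrument has no earlier value to use.

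The child's view is one of the three in the primary outcome. A child who answers a form put to them by a parent who was trained in the method, and who may have delivered the story, has some reason to answer favourably.

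Section 2.1 makes progress to a full trial depend on meeting the objectives, and acceptability is one of them. A rating drawn mainly from those who stayed could make that case look stronger than it is. An analysis plan cannot recover ratings that were never collected.

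**Working it through.** **The plan's only precision figure.** Section 3.3.10 says that 50 participants estimate an 85% recruitment rate to within 10% with 95% confidence. Check: 1.96 × √(0.85 × 0.15 / 50) = 0.099, or 9.9 points. It reproduces, but it concerns recruitment. The protocol gives no figure for acceptability or dropout and no cut-off on the Intervention Rating Profile.

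**Who can give an end-of-study rating:**

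1. A family that stops the stories but stays in follow-up can (section 3.3.7).
2. A family that leaves follow-up, or all aspects of the study, does not unless it is re-contacted (sections 3.3.7 and 3.3.12).
3. A family in follow-up that does not return the form does not.
4. Teachers rate separately, so a family's departure need not remove the teacher's rating.

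The gap is therefore groups 2 and 3, not everyone who rejects the intervention.

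**Whether the interviews fill it.** They come after the story is written, with no later point fixed, so they need not reflect months of use. A family that stops before a story exists has no defined interview point. The sampling list is open but does not name stopping or low use. Reasons for discontinuation are explicitly sought only from those delivering the intervention, which for other families is second-hand.

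**Size under assumptions.** Let m be the share not rating, p_r the approval among raters and p_n the approval among non-raters.

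- Approval among all allocated = p_r(1 − m) + p_n·m
- Overstatement = p_r minus that = m(p_r − p_n)

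Assume p_r = 80%. Overstatement in percentage points:

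| m | p_n = 80% | p_n = 50% | p_n = 20% | p_n = 0% |
|---|---|---|---|---|
| 10% | 0 | 3 | 6 | 8 |
| 15% | 0 | 4.5 | 9 | 12 |
| 20% | 0 | 6 | 12 | 16 |
| 30% | 0 | 9 | 18 | 24 |

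In counts, with the 25 intervention children of the Summary and 20% not rating: 20 rate and 16 approve, so 16/20 = 80% is reported. If none of the other 5 approves, the figure for all allocated is 16/25 = 64%, a gap of 16 points. If all 5 approve it is 21/25 = 84%, and the reported figure is 4 points too low. The sign thus depends on the non-raters being less favourable.

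For scale, the 95% half-width for 80% in 25 children, ignoring clustering by school, is 1.96 × √(0.8 × 0.2 / 25) = 0.157, or 15.7 points.

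No comparable calculation is possible for the child's form. The protocol gives nothing from which to size the effect of parent administration.

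**The case against.** A reader might infer that acceptability is measured only at the end, that those who reject the intervention are necessarily missed, and that a toolkit many had abandoned could be reported as highly acceptable. The documents do not support this:

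- The primary outcome also rests on interviews, held after the story is written, that ask about acceptability of the treatment.
- Stopping the intervention is not leaving follow-up. Section 3.3.7 keeps such families in data collection, and section 3.3.12 adds attempts to reach those lost.
- Sections 3.3.5 and 3.3.14 provide for recording attrition and non-compliance, so widespread abandonment would be visible.
- The sampling characteristics are given as examples, so discontinuers could be chosen.

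Nor does the child's view come only through the parent. Children are interviewed too, though with family members. Parent administration is a practical choice for ages 4-15 with learning disability included. The child's form has no stated time point, so it cannot be called end-only.

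All of this stands, and it narrows the point without removing it. An attrition count does not show whether people left because they found the intervention unacceptable. An open sampling list does not commit the team to hearing from those who stopped. Neither route to the child's view is stated to be independent of the family.

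**Conclusion.** The concern holds as a risk, not as a demonstrated bias. The only rating scale for acceptability to parents and teachers misses those who leave follow-up or do not respond, and the interviews repair this only in part. The parent-administered child form adds a further risk of favourable answers, of unknown size.

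For the rating scale, the overstatement is between 0 and 24 points, assuming 10-30% non-response, 80% approval among raters and non-raters no more favourable than raters. At 20% non-response it is 6 to 16 points if between half and none of the non-raters approve. The upper end is about as large as the sampling error in 25 children and, unlike that error, does not shrink with more recruits. Treating every non-rater as a rejecter is the extreme case and should not be read as the expected one. The point merits a cheap improvement and does not undermine the feasibility design.

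**What to change.** 1. **Section 3.3.14.** Offer the Intervention Rating Profile, on a voluntary basis, at the contact where section 3.3.7 has the type of withdrawal clarified, as well as at the end of the study. Report acceptability beside the number allocated and the number who gave no rating.
2. **Section 3.3.13.** Add discontinuation or low use to the purposive sampling characteristics, within the 10 intervention-arm interviews already planned.
3. **Section 3.3.14, item 6.** Where it needs no extra staff, let children who are able complete their own form instead of answering through the parent. Having a researcher administer it would cost staff time and is not needed to meet the main point.

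The cost is one short extra form at a contact that the protocol already implies, and fewer interview places for families who complete the intervention.
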